Following informed and written consent, eligible participants will be randomised within 2 working days. Our Clinical Trials Unit will support the development of the randomisation algorithms and the web-based technology. Randomisation will be in the ratio 1:1:1 to the three groups and will be stratified by centre and family contact (since participants who do not have regular contact with their families will not receive the family intervention components of psychological intervention, although they will still be included). Randomisation (at the individual level) will be independent and concealed, using randomised-permuted blocks of random size administered via a study-specific web-based system developed by the CTU. The allocation is made known to the trial manager (to monitor adherence to the randomisation algorithm), the trial administrator and trial therapists by email and SMS text message. The allocation code will be maintained for research assistants until all outcome measures for all participants have been collected.

Protection against bias

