Single blind – assessors will be blind to treatment condition. Blindness will be maintained using a wide range of measures which we have implemented successfully in other single blind trials (EDIE 2; ACTION; FOCUS). These include separate offices for the therapists and research assistants, protocols for answering telephones including reminders for clinicians, participants and family members about the blind, protocols for message taking and secretarial support, separate diaries and pigeon holes and data file security, using passwords and encryption of randomisation information. We will develop a standard operating procedure (SOP) for maintaining, recording and managing blinding, which will outline all of these procedures. This SOP will be reviewed by, and agreed with, our data monitoring committee (DMC)/ trial steering committee (TSC). Each researcher will sign this SOP to confirm they understand and will comply with the blinding procedures. All blind breaks will be recorded by the trial manager and reviewed by the Chief Investigator for patterns in unblindings. There is only one follow-up scheduled during the intervention window (at 3 months). This will reduce the risk of blind breaks occurring because of therapists and RAs crossing paths for visits and it will reduce the opportunity for unblinding to occur because of communication with participants to arrange visits. Maintaining rater blindness to treatment allocation is crucial, and the DMC and TSC will regularly monitor unblindings by each centre, and implement corrective action if necessary. Following eligibility assessment and completion of baseline assessments, participants will be allocated to treatment groups through our web-based randomisation service and the Trial administrator will inform the participants of this decision. All letters to participants and clinicians will contain a standardised statement about the need to maintain the single blinding process. Any accidental unblindings will be recorded. Where possible, we will identify an independent assessor with whom the blind has not been broken to complete subsequent follow-ups, subject to any threats to participant engagement with follow-up. Given each intervention is provided in two arms of this three-arm trial, the blind will also be easier to maintain than in our previous two-arm trials.

Concomitant therapy

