As this is a feasibility trial, a single primary outcome is not meaningful and the key outcomes to inform a future trial are referral rates, recruitment, attendance at therapy sessions, compliance with medication and follow-up and questionnaire response rates. Acceptability of treatment will be measured using rates of drop-out from treatment.

Secondary outcomes:

All secondary outcomes are being collected to determine their suitability for use in a subsequent trial, rather than to draw conclusions about safety or efficacy of treatments.

The proposed primary outcome measure for a subsequent definitive trial will be total PANSS score (4), a commonly used outcome in psychosis trials, allowing comparison with wider evidence. The PANSS is a 30-item rating scale designed to provide a comprehensive assessment of psychopathology in adults with a diagnosis of schizophrenia. Five components have been reported: positive, negative, depression-anxiety, agitation-excitement, and disorganisation.

In order to test the acceptability and usefulness of potential secondary outcome measures in a trial context, we will also assess: i) social/educational/occupational functioning ii) self-rated

recovery iii) dimensions of psychotic symptoms. Adverse effects (weight gain, sexual dysfunction, metabolic effects and extrapyramidal effects) will be systematically assessed. Hospital admissions, serious adverse events and dose of APs and PIs will also be measured in all groups

Social/educational/occupational functioning

Social and educational/occupational functioning will be assessed using the First Episode Social Functioning Scale (FESFS) (28). The FESFS was developed with over 200 individuals receiving services in first episode psychosis clinics. Subscales include: Friendships and social activities, Independent living skills, Interacting with people, Family, Intimacy, Relationships and social activities at work, Work abilities, Relationships and social activities at school, Educational abilities. This measure has good reliability, convergent and discriminant validity and sensitivity to change. We will also assess time use in constructive economic activity.

Recovery

Recovery will be assessed using the questionnaire about the process of recovery, a user-defined measure (QPR (29)), which is a 15-item questionnaire developed collaboratively with service users with psychosis, measuring subjective recovery.

Dimensions of Psychotic Experiences

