All outcome measures will be administered at baseline and subsequently at 3, 6 (end of treatment) and 12 months by research assistants who will have been trained in the use of all the instruments and scales, to achieve a satisfactory level of inter-rater reliability. Regular training sessions including the use of video and role play will be conducted with all research assistants in order to maintain reliability and prevent rater drift. Participants will be offered choices regarding length of assessments, including the option of breaks and multiple

occasions. Assessment measures will be clearly prioritised so that the most important will be collected first to avoid missing data. We will have a standard protocol for managing any distress that is associated with the completion of measures, which we have successfully utilised in several trials and has been developed in collaboration with service users; this includes telephone contact within 48 hours of assessments in order to check on participant well-being. We will send participants a thank you card at the end of their planned involvement trial as a token of our appreciation of their involvement. For participants who withdraw from the trial, on withdrawal we will ask them if they wish to be sent a thank you card. If they decline then they will not be sent a thank you card.

Data analysis:

The main aims of the feasibility trial will be delivered both via the continued monitoring of descriptive data and the analysis of data at the end of the last follow-up assessment. Analysis will take place after full recruitment and follow-up (i.e. there will be no interim analyses for efficacy, although an independent Data Monitoring Committee will monitor trial progress and any safety issues on a regular basis).

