Each site will have a weekly team meeting to ensure regular communication and interaction between site leads, local clinicians and research assistants (measures will be followed to avoid blind breaks). There will be monthly trial management meetings with all applicants via video conference, with 6 monthly extended face-to-face meetings. The trial manager will conduct weekly telephone supervision with all research assistants that will focus on recruitment, liaison with referrers, compliance to follow-ups, and specific scoring queries for interview based measures. In addition, they will chair a fortnightly teleconference that focuses on interrater reliability across sites and recruitment during the recruitment window to share best practice and recruitment issue problem solving. The psychological therapists will receive weekly supervision from a central clinical supervisor based in Manchester, which will be focused on fidelity and adherence to the protocol and model. Supervision from site leads focussed on problem solving, risk management and local issues will supplement this. Quarterly triadic supervision involving supervisee, central supervisor and site leads will be used to ensure these arrangements operate smoothly. We have used these processes successfully in several previous multisite RCTs of psychological interventions.

Data management

Each study participant will be assigned a unique trial identification number at the start of the assessment process. This number will be written on all clinical assessment forms/datasheets and databases used to record data on study participants. A hard copy of a record sheet linking patient identity, contact details and trial identification number for all participants will be kept at each site. It will be placed securely in a locked filling cabinet separate from datasheets. This will be also stored in an electronic database, which will be accessible to authorised users at the sites via the study web portal hosted at CHaRT (it will be password protected and secure). The local study co-ordinator will enter the data on to an electronic database, and all such data will be checked for errors before being transferred to the appropriate statistical package. All data will be kept secure at all times and maintained in accordance with the requirements of the Data Protection Act, and archived according to clinical trial GCP regulations.

Approval by ethics committees

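### The trial manager knows each participant's arm and also handles the masked raters' scoring queries, which leaves one indirect route from allocation to interview-rated scores

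*Protocol*

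**What the plan says.** The Randomisation section names those who learn the allocation: "The allocation is made known to the trial manager (to monitor adherence to the randomisation algorithm), the trial administrator and trial therapists". The only reason given for including the trial manager is monitoring of the algorithm. The same section protects the raters: "The allocation code will be maintained for research assistants until all outcome measures for all participants have been collected".

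Communication within and between sites sets out the trial manager's contact with those raters: "The trial manager will conduct weekly telephone supervision with all research assistants". Recruitment, liaison with referrers and follow-up compliance are on the agenda, together with "specific scoring queries for interview based measures". The section adds that "they will chair a fortnightly teleconference that focuses on interrater reliability across sites"; that call also deals with recruitment.

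The section on assessment schedule and administration says who collects the outcomes: "All outcome measures will be administered at baseline and subsequently at 3, 6 (end of treatment) and 12 months by research assistants". Secondary outcomes adds: "The proposed primary outcome measure for a subsequent definitive trial will be total PANSS score".

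Protection against bias says: "Maintaining rater blindness to treatment allocation is crucial". It lists physical and procedural separation of therapists from research assistants, data security, a signed blinding SOP still to be written, recording of blind breaks by the trial manager, and a replacement assessor after an unblinding where possible.

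**The concern.** Masking of raters protects a rating scale only if whoever helps to settle the rating is masked too. Here one role holds both the allocation of each participant and the task of answering scoring queries. Advice on a borderline item could lean one way in one arm and another way in the next, even without intent, while the research assistant remains formally blind.

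Such an influence would leave no trace. It is not an unblinding, so the log would not show it, and neither would the review of that log by the Chief Investigator, DMC and TSC. It also could not be removed from the recorded ratings afterwards.

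Two uses of the PANSS are exposed. Under Data analysis, the PANSS is modelled over time and reported by group with 95% confidence intervals, to inform the later trial. Under Procedures for deterioration, a worsening of more than 12.5% at 3 months bears on whether a monotherapy participant goes into the combined arm. A leaning in the scores could therefore touch treatment received as well as estimates.

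**Working it through.** No stated figure bears on this point and there is nothing to recompute. The check sets the relevant sections side by side.

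1. **Does the trial manager know individual allocations?** Yes. Under Randomisation the notification goes out by email and SMS, with no exception by site and no statement that the trial manager sees it only in unlinked form.

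2. **Does the trial manager deal with scoring?** Yes. Under Communication within and between sites, scoring queries are one of four supervision topics, weekly, for all research assistants. The fortnightly reliability call is a second contact.

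3. **Is the PANSS among the measures concerned?** Presumably. That section speaks of interview-based measures without naming any. The PANSS is described under Secondary outcomes as a 30-item rating scale, and research assistants administer all outcome measures. This step is an inference.

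4. **Which assessments can be reached?** Those at 3, 6 and 12 months. Protection against bias places allocation after the baseline assessments, so baseline ratings are out of reach unless a query on them is settled after randomisation.

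5. **Does a listed safeguard close the route?** None does.
   - Separate offices, diaries and pigeon holes keep raters from therapists.
   - Telephone and message protocols, reminders and standard letters deal with clinicians, participants and families.
   - Passwords and encryption deal with files.
   - A replacement assessor deals with a rater who has been unblinded.
   - The SOP is described as setting out these same procedures.

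   Nothing says that queries are de-identified, that a masked person resolves them, or that the trial manager is kept apart from scoring.

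6. **Does it touch the go/no-go decision?** No. The four feasibility success criteria are recruitment, retention at 6 months, attendance at 6 or more CBT sessions, and 6 consecutive weeks of antipsychotic exposure. None uses a PANSS value.

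7. **Is the trial manager's knowledge of allocation necessary?** Not on the stated reason. The CTU develops the web-based randomisation system and supports its algorithm. The trial administrator already receives allocations and tells participants the result.

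**The case against.** The strongest reply is that the raters are masked, stay masked to the end, and are shielded by a serious set of procedures. A reader might infer from the overlap of roles that the PANSS is unprotected from knowledge of allocation. The documents do not support that: one indirect route is open, and the direct ones are addressed.

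The mechanism is also partly inferred. The protocol does not say that queries identify the participant, that the trial manager decides the score, or that the reliability call discusses live cases; reliability is elsewhere said to be maintained through training with video and role play. The list of safeguards is introduced as examples, and the unseen SOP might add to it. This lowers certainty about how often the route would be used. It does not close the route, because the protocol fixes both roles and describes the SOP only by reference to the procedures listed.

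The trial's purpose counts too. Secondary outcomes are collected to judge their suitability, with efficacy and safety conclusions disclaimed. A reader might conclude that the flaw threatens the feasibility decision or the evidence that blinding is feasible. It does not reach the progression criteria, and blinding is neither one of those criteria nor a listed objective. The by-arm estimates are nevertheless planned and meant to inform the definitive trial, so a narrower relevance stands.

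Finally, a reader might want a size. An assumed shift of 2 to 3 PANSS points over an assumed SD of 15 gives 2/15 = 0.13 to 3/15 = 0.20 SD. The protocol supplies neither input, and nothing in it shows that queries are frequent or advice consistently directional. The quotient only restates the assumptions and should not be cited as a magnitude.

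**Conclusion.** The point holds as a single gap in the blinding arrangements. A person who knows the arm handles scoring queries from all research assistants and chairs the reliability call, and nothing in the protocol separates the two roles. The exposure is to post-randomisation interview ratings, and so to the by-arm PANSS estimates and the 3-month deterioration trigger. Neither the size nor the direction of any bias can be derived from the document.

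The conclusion rests on two assumptions: that the PANSS is among the queried measures, and that at least some queries can be linked to a participant. It is a cheap improvement of moderate severity, well short of a defect that invalidates the trial.

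**What to change.** Preferred change:
- Remove the trial manager from the allocation notification.
- Let the CTU, which already provides the randomisation system, monitor adherence to the algorithm.
- Let the trial administrator handle tasks that depend on the allocation.
- Have blind breaks logged without the arm, or by the administrator. Otherwise the trial manager, who records them all, could learn allocations again by that path.

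Alternative, if the trial manager must stay unblinded: an existing masked team member resolves de-identified scoring queries and chairs the reliability call. The protocol has no designated masked lead for rating, so this is cheap only if someone already in the team can take it on.

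Either way, state the choice in the protocol and in the blinding SOP. The cost of the preferred change is an amended notification list and a few lines of text, with no new staff. The small downside is that the trial manager must route allocation-specific questions through the administrator or the CTU.
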